stimulus. Following the disappearance of the target, feedback is provided as to the amount of money won for correct responses to the target (responding while target is displayed). An incorrect response is also indicated. Feedback is followed by a variable inter-trial interval (ITI). Each cue is presented an equal number of times in a pseudo-randomized order. Following completion of the session, participants will be told that they won \$35 during the task (the amount is fixed at \$35 to ensure that all participants receive the same amount irrespective of performance capacity).

Pulsed Arterial Spin Labeling (PASL): Since it is not known if cannabis or dronabinol will induce neurovascular changes, we will use PASL²⁰³⁻²⁰⁹ to characterize resting regional cerebral blood flow (CBF) during each scan session.²¹⁰⁻²¹² ASL methods measure CBF by using water in arterial blood as an endogenous tracer.^{206, 213} PASL, which alternates control and labeling scans that are then compared to quantify perfusion,^{214, 215} will be implemented.²¹⁶ Derived perfusion images will be coregistered to the fMRI and anatomic scans and analyzed by tissue compartment and project-specific ROIs. Masks derived from segmented anatomic maps will be used to estimate global and local gray matter and white matter perfusion values. Perfusion will also be determined for the same ROIs targeted in the fMRI experiments.

fMRI Paced Motor Task (PMT): Participants will complete a visually-triggered sequential finger movement fMRI task in which periods of finger movement alternate with rest for a total of 8 minutes.

Structural MRI Imaging Parameters: Structural scans will be acquired during the baseline scan session only. We will also acquire survey images as a screen for focal lesions. T1-weighted anatomic reference images will be acquired in the same planes and thickness during each scan session. The magnet's repositioning system will be used to ensure comparable head positioning across the scan sessions.

Eye Camera: We will use an MRI-compatible camera with integrated LED infrared light (MRC Systems, Germany; model 12M-I) that can be used inside the bore of the scanner. This will allow us to monitor and record participant's eyes to determine whether they are keeping them open/closed per instructions during the scan session. The camera is based on a single light-emitting-diode (LED) which is embedded in the titanium housing and emits diffuse light.

GENETIC TESTING

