Safety Assessment - Participants in Groups 1-3 and Groups 5-7 will have a baseline medical history and physical assessment to rule out medical contraindications to administration of dronabinol or cannabis. The assessment will include blood pressure, electrocardiogram (EKG), complete blood count and blood chemistry screen. All women in the study will have a pregnancy test at screening and before the scan on each scan day. Adverse events and medications that participants are receiving outside of the course of the study will be tracked and reviewed at each visit.

Other: The Behavior Rating Inventory of Executive Functions - Adult version (BRIEF-A) will be administered to gauge subjective integrity of executive functions in everyday life over the past month (Roth, Isquith, Gioia, 2015). This 75 item questionnaire takes about 10 minutes to complete. Participants will complete the measure once at the T1 session.

11. Deception.

Will deception of participants, including withheld information, be used in this research?

Yes No

If yes, complete a-d.

a) Describe the deception being used in this study:

The nature of the monetary incentive delay task and probabilistic reward task requires subjects to respond believing the speed of their response is linked to the money they earn. However all participants will receive \$35.00 for completing each of the two fMRI monetary incentive delay tasks and a total of up to \$50 for completing the three

probabilistic reward tasks, regardless of their task performance (which is based on accuracy and speed) . The instructions participants are given for the task, however, do not indicate this, but rather only say that they can win money based on their performance.

b) Explain why deception is necessary in this research:

We decided to fix the amount of winnings on each task, and thus deceive participants, so as to not disadvantage the participants with schizophrenia who tend to respond more slowly and with less accuracy than normal controls because of their illness (or related issues such as medications). Participants will not be aware that everyone receives the same amounts because it is essential in the study of reward circuitry that they believe they are "winning" additional funds, and that their winnings are dependent upon performance. This technique is used routinely by researchers across the world in order to study brain reward circuitry. Use of the same technique allows researchers to compare results across studies.

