c) Describe the information provided to subjects when they decide to participate:

As stated above, the instructions participants are given for the task say that they can win money based on their performance.

d) Describe how the subjects will be provided with additional pertinent information after participation (debriefing):

We will simply let participants know how much money they "won". We cannot debrief participants and tell them that the earnings were fixed because we believe that participants may tell other participants and that this knowledge would then interfere with the consistent measurement of brain reward circuitry between patients.

12. Enrollment:

a) Estimated number of participants for duration of entire study:

At Dartmouth or associated sites: Female: 100 Male: 300

If Multi-center study: Estimated total number at all sites: 400

b) Estimated age range of participants: 18-55

13. Timetables:

a) Indicate length of participant involvement in the study: Approximately 4-6 weeks

b) Estimate how long it will take to enroll enough participants to complete this study: 5 years

14. Risks:

The purpose of this section is to determine if subjects will be placed "at risk," which in general means

exposed to the possibility of physical, psychological, social, economic, legal, dignitary or other harm as a consequence of any activity proposed in the research project.

a) What is the overall risk classification of the research?

- Minimal
- Greater than minimal
- Significant
- Unknown

Note: In the federal regulations on human subjects protection minimal risk means "The probability and magnitude of harm or discomfort anticipated in the research are not greater in and of themselves than those ordinarily encountered in daily life or during the performance of routine physical or psychological examinations or tests."

b) Describe any potential risks (physical, psychological, social, legal, economic, or other) and assess their likelihood and seriousness. Describe the procedures for protecting against or minimizing these risks, including risks to confidentiality, and assess their likely effectiveness. Please list risks from most severe/likely to least severe/unlikely.

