- \$35 will also be "won" on the T1 Test Day for the monetary incentive delay task paid as a check at the end of the study - NOTE: This amount is not disclosed to participants because it would invalidate the testing.
- \$200 for T2 Scan day paid as a check at the end of the study
- \$35 will also be "won" on the T2 Scan day for the Monetary Incentive Delay task paid as a check at the end of the study
- Participants will "win" between \$15-\$20 for completing the Probabilistic Reward Task. Over the three sessions, this would not total more than \$50. We do not state the exact amount in the consent because it invalidates the testing.

Total = \$495: \$375 paid as stipends and \$120 that is "won"

All participants in Groups 5-7 (CUD only) will be paid:

- \$50 for completing the Screening Visit paid as a gift card on the day of the visit
- \$50 for the Neuropsych Baseline Visit paid as a check at the end of the study
- \$400 for T1 Scan day paid as a check at the end of the study
- \$35 will also be "won" on the T1 Test Day for the monetary incentive delay task paid as a check at the end of the study
- \$500 for T2 Scan day paid as a check at the end of the study
- \$35 will also be "won" on the T2 Scan day for the Monetary Incentive Delay task paid as a check at the end of the study
- Participants will "win" between \$15-\$20 for completing the Probabilistic Reward Task. Over the three sessions, this would not total more than \$50.

Total = \$1,120: \$1,00 paid as stipends and \$120 that is "won"

All participants in Group 8 (Healthy Control) will be paid:

- \$50 for completing the Screening Visit paid as a gift card on the day of the visit
- \$50 for the Neuropsych Baseline Visit paid as a check at the end of the study
- \$200 for T1 Scan day paid as a check at the end of the study
- \$35 will also be "won" on the T1 Test Day for the monetary incentive delay task paid as a check at the end of the study
- \$200 for T2 Scan day paid as a check at the end of the study
- \$35 will also be "won" on the T2 Scan day for the Monetary Incentive Delay task paid as a check at the end of the study
- Participants will "win" between \$15-\$20 for completing the Probabilistic Reward Task. Over the three sessions, this would not total more than \$50.

Total = \$620: \$500 paid as stipends and \$120 that is "won"

In addition, all but Groups 4 and 8 can earn money for being abstinent from alcohol or drugs.

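### Announcing the fixed $35 after the T1 reward task may weaken, before the T2 run, the pay-for-performance belief that the task depends on

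*Combined protocol and SAP*

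**What the plan says.** Section 4 (MID Task) describes cues that show what can be won or lost on a trial. After each target, "feedback is provided as to the amount of money won for correct responses to the target", and errors are shown as well. It then states: "Following completion of the session, participants will be told that they won" $35. The sum is fixed "to ensure that all participants receive the same amount irrespective of performance capacity".

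Section 11(a) confirms that the $35 is given "for completing each of the two fMRI monetary incentive delay tasks", so it applies at T1 and at T2. Section 11(b) holds it essential that participants believe they are winning money "and that their winnings are dependent upon performance", and adds: "Participants will not be aware that everyone receives the same amounts". On debriefing, Section 11(d) begins "We will simply let participants know how much money they" won, and declines to reveal that the earnings were fixed.

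Section 29 (Participant Remuneration) pays the MID winnings from both scan days by check when the study ends. In the list for Groups 1-4 it notes beside the T1 amount: "This amount is not disclosed to participants because it would invalidate the testing".

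Section 7(b) tests Aim 2a with a Group by Time analysis of T1 and T2, covering G1, G3, G4, G7 and G8, and in the same way for G2.

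**The concern.** The plan uses deception to protect one belief: that faster and more accurate responding earns more. The belief has to last until the T2 run, because that run supplies the second half of the Aim 2a comparison. Between the two runs, however, the plan gives each participant a total that does not come from their own responses, and they can set it against the feedback they remember.

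Someone who remembers winning clearly more or less than $35 has a reason to doubt the contingency before the second run. If doubt lowers reward anticipation at T2, there is less of a signal for cannabis or dronabinol to change. The plan describes no question or other check that would show whether participants still believed the contingency at T2.

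**Working it through.** **1. The plan's own figure.** Section 29 gives $120 as the total that is won. Two MID payments plus the ceiling for the Probabilistic Reward Task give 35 + 35 + 50 = 120, which agrees. The same $35 therefore applies on both scan days.

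**2. Order of events.** From Sections 4 and 29: T1 MID run; $35 announced; an interval with a target of 7 days, a minimum of 2 and no maximum; T2 capsules and cigarette (Groups 1-3 and 5-7); T2 MID run; $35 announced; payment by check at the end. Before the T2 run a participant has heard one MID total. The second, identical figure comes too late to affect that run. The T1 MID data used for Aim 1 are collected before any announcement and are not touched.

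**3. What a participant can compare.** Feedback follows performance; the announced total does not. The plan does not say whether the task is set up so that feedback comes out near $35. Cue values, trial numbers, hit rates and any running total are not given. A mismatch is therefore possible for any participant, but its size and frequency cannot be calculated.

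**4. Consequence by contrast**, supposing that some participants do lose belief:

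| Contrast | Who hears $35 after T1 | Expected consequence |
|---|---|---|
| G1 or G2 v G3; G5 or G6 v G7 | Every arm, before any study drug | Loss is shared; a true effect may be diluted |
| G1 or G2 v G4 | Both; same schizophrenia diagnosis | A shift tied to diagnosis would go the same way in both |
| G1 or G2 v G7 or G8 | Both; diagnosis differs | Unequal shift possible, not shown |

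On the last row the documents point both ways. Section 11(b) expects slower and less accurate responses in schizophrenia. Section 3, reviewing MID studies, says that patients without a substance use disorder perform this task normally.

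**5. The non-disclosure note.** In the same Section 29 list, the exact Probabilistic Reward Task sum is said to be left out of the consent form because stating it would invalidate testing. The natural reading is that the MID note also concerns disclosure in advance. On that reading it is compatible with naming the amount afterwards (Sections 4 and 11(d)). What it leaves open is how long the silence lasts. For the T2 run, a total announced after T1 is advance information about how the task pays.

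**6. Whether the T1 announcement is needed.** Both MID sums are paid at the end of the study, so payment does not require a figure at T1.

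**The case against.** The strongest reply is that participants hear an amount, and nothing more. They are not told that it is fixed, the same for all or unrelated to their hits; Section 11 withholds exactly that. To lose belief they would have to keep a rough tally of wins and losses in the scanner and then notice a discrepancy. This stands, and it is why the point is that belief may be weakened. A reader might infer that the belief is in fact broken before T2; the documents do not show that.

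A reader might also infer that over-credited patients and under-credited controls would converge at T2 and so mimic amelioration. That is not supported. G4 has the same schizophrenia diagnosis as G1 and G2, and G3 hears the same $35 as they do. Section 7(b) keeps G3 in the same analysis and also compares G3, G4, G7 and G8 directly, so convergence without drug should show there. The statement in Section 3 about normal task performance also weakens the premise.

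Nor do Sections 4 and 29 plainly contradict each other, given the advance-disclosure reading. The refusal to debrief in Section 11(d) rests on participants talking to one another, not on carry-over within one person. Whether the announcement precedes the Probabilistic Reward Task, which follows the scanner, depends on what Section 4 means by the session, and that is not settled.

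Finally, withholding the T1 total could itself make the money seem less real, particularly as the interval to T2 has no maximum. This has little weight: trial feedback still shows winnings, and payment already comes at the end.

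**Conclusion.** The point holds in a limited form. A performance-independent total is announced between the two MID runs of Aim 2a, where it can only put at risk a belief that the plan calls essential, and payment does not require it then. The expected harm in the randomised contrasts is possible dilution of a drug effect. A false drug effect there is not expected. An unequal effect against G7 or G8 remains possible and unproven.

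No magnitude can be given. Any figure for lost power or for false-positive rate would need hit rates, cue values and a share of disbelieving participants, none of which the documents supply. The conclusion rests on two readings: that the announcement follows each MID session, T1 included, and that some participants may compare it with their feedback. It is a worthwhile, inexpensive improvement and not a flaw that invalidates the design.

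**What to change.** - **Section 4 (MID Task):** give no MID total at T1. Tell participants only that their winnings will be paid with the end-of-study check. Announce the totals once, after the last reward task on the T2 day.
- **Section 11(d):** say that participants learn how much they won at that single point.
- **Section 29:** state that non-disclosure of the amount covers the period up to the end of T2 testing.

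This is one sentence in the protocol and the task script, plus two matching edits. Payment amounts and dates, the task itself and the analysis stay as they are. The downside is that participants wait until T2 to hear their T1 winnings.

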7. Currently stable in treatment (either on an antipsychotic or not) for the past month as determined by a study physician's review
8. Not seeking treatment for their CUD.

Group 4 - Control participants with SCZ

1. Ages 18 – 55 years old, inclusive
2. Diagnosis of schizophrenia or schizoaffective disorder as confirmed with the SCID
3. Willing to remain abstinent for the 7 days before the baseline assessments and for 14 days before the two scan days. Note: If the 14 day period of abstinence is reduced for the groups with a CUD, it will be reduced for Group 4 also.
4. Psychiatrically stable as indicated by being treated as an outpatient for the past month, as determined by a study physician's review

5. Currently stable in treatment (either on an antipsychotic or not) for the past month as determined by a study physician's review

Groups 5-7 - Control participants with CUD

1. Ages 18 – 55 years old, inclusive
2. Diagnosis of cannabis abuse or dependence as confirmed by the SCID
3. Use of cannabis within the month prior to screening based on the TLFB
4. Willing to remain abstinent for 7 days before the baseline assessments and 14 days before the two scan days. Note: If the 14 day period of abstinence is too great a barrier for participants, the PI may decrease the amount to 7 days.
5. Not seeking treatment for their CUD.

Group 8 – Healthy control participants

1. Ages 18 – 55 years old, inclusive
2. Willing to remain abstinent for the 7 days before the baseline assessments and 14 days before the two scan days. Note: If the 14 day period of abstinence is reduced for the groups with a CUD, it will be reduced for Group 8 also.

Exclusion criteria:

Groups 1-3 with SCZ-CUD

1. Positive symptoms of psychosis (> 4 [moderate]) on any item of the PANSS psychosis subscale (once abstinent) except for the hallucination item. We will exclude for a rating > 5. for this item.
2. Current cocaine/stimulant dependence. (Note: Current alcohol, synthetic cannabis, nicotine, and caffeine abuse or dependence are allowed; current cocaine/stimulant or other drug abuse is allowed provided the person can achieve the required abstinence; past dependence on cocaine/stimulants or other drugs is also allowed)
3. Pharmacological treatment for addiction (e.g., disulfiram, naltrexone, acamprosate, topiramate, varenicline, bupropion) as determined by a study physician's review.
4. Mental retardation

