Aim 1 (Time 1 Group Differences): To determine whether at T1 dual diagnosis patients with SCZ-CUD (G1 - G3 combined) show (as compared to normal controls, G8):

- reduced fMRI activation of BRC (particularly the nucleus accumbens) to anticipation of monetary reward, as determined via group mixed effects ANOVA on contrasts of interest (e.g., anticipating reward > anticipating no reward);
- decreased resting state connectivity within the BRC as evaluated using the Statistical Parametric Mapping Version 8 (SPM8) mixed effects ANOVA on the Fisher-transformed r value connectivity maps derived from the nucleus accumbens seed ROI; and
- impaired reward responsiveness as determined using mixed effects ANOVA on response bias scores.

In addition, we will use a group mixed effects ANOVA to explore whether they will also differ from control participants with SCZ alone (G4) and control participants with CUD alone (G5, G6 and G7) on these measures.

Aim 2a and 2c (Group by Time effects on MID and BRC related to cannabis or dronabinol): Below, we describe the analyses involving dual diagnosis patients given cannabis (Group 1 -- G1); the same pattern of analyses will be carried out for the patients given dronabinol (Group 2 -- G2). Similar analyses will also be carried out for participants with CUD alone (Groups 5, 6 and 7 – G5, G6 and G7).

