The two sets of intervention effects (specific to SCZ-CUD and CUD alone) will be compared. To determine whether the dual diagnosis patients given cannabis (G1) will show differential changes in fMRI activation in specific ROIs within BRC and in RSC within the BRC between T1 and T2, we will first conduct a Group (G1, G3, G4, G7, G8) by Time (T1, T2) mixed-model repeated measures ANOVA. Predicting a significant omnibus ANOVA, we will next examine planned contrasts to address specific hypotheses: To determine whether cannabis ameliorates BRC dysfunction, we will compare brain activation/connectivity in the patient group given cannabis (G1) to that of the control groups (SCZ-CUD placebo [G3]); (SCZ alone [G4]; CUD alone placebo [G7]; and normal controls [G8]) using a Group (G1, G3, G4, G7, G8) by Time (T1, T2) mixed-model ANOVA followed by pairwise comparisons. The inclusion of Group 4 in this analysis will allow us to examine whether any significant cannabis effect on BRC in Group 1 (G1) is independent of any changes due to repeated testing specific to having a diagnosis of SCZ. Lastly, although not a primary hypothesis of interest, to further explore any potential placebo effect on BRC, we will also conduct a comparison of G3, G4, G7 and G8.

Aim 2b and 2c (Group by Time effects on RR related to cannabis or dronabinol): To explore whether the patients with SCZ-CUD who received cannabis (G1) will show differential changes in RR between T1 and T2 relative to G3, G4, G7 and G8, we will proceed as above for Aim 2a to assess response bias, and analogously for participants who received dronabinol (G2). Similar analyses will be used for Groups 5, 6, 7 and 8, with results compared to those obtained for patients with SCZ-CUD.

Although not aims of the study, we will assess the relationship between THC plasma levels and changes in BRC activation/connectivity following cannabis (G1 or G5) and dronabinol (G2 or G6) using covariance modeling in SPM8; we will conduct analyses to determine whether cannabis (G1 or G5) and dronabinol (G2 or G6) have comparable effects on fMRI BRC activation/connectivity using a Group (G1 or G5, G2 or G6) by Time (T1, T2) mixed-model ANOVA; and we will use cerebral blood flow values obtained from arterial spin labeling MRI as covariates in the ROI analyses of BOLD data to control for any artifactual changes in fMRI signal related to drug-induced influences on CBF.

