Diagnosis: We will do an all-source Structured Clinical Interview for DSM-IV-TR (SCID)¹⁵⁷ to ensure each participant meets the appropriate diagnostic criteria for his or her group. Use of the DSM-IV will allow us to have a consistent measure across both the previous pilot study and this one (and the DSM-5 SCID is not yet available). The SCID-II module for Antisocial Personality Disorder will be used to detect whether or not participants meet criteria for this disorder. Research suggests that trauma may change reward circuitry. We will therefore track trauma exposure using the PTSD Screening Questionnaire and use these data as covariates in our final analyses.

Substance Use: We will use the Timeline Follow-Back (TLFB) calendar to establish use of cannabis or other substances following the recommended method of Sobell.¹⁷³

Psychiatric symptoms: We will use the PANSS (Positive and Negative Syndrome Scale)¹⁷⁴ to assess psychiatric symptoms, as well as positive and negative symptoms. The Barkley Adult ADHD Rating Scale-IV (BAARS-IV; Barkley, 2011) will be administered during the Baseline Neuropsychiatric Testing visit to assess current symptoms of attention deficit.

Neurological symptoms: Extrapyramidal system effects will be assessed with the Simpson-Angus Scale (S-A),¹⁷⁵ the Abnormal Involuntary Movements Scale (AIMS),¹⁷⁶ and the Barnes Akathisia Scale.¹⁷⁷

Cannabis-related effects: We will employ a brief version of the visual analogue self-report scale (VAS) used by our consultant, [name], in her studies of cannabis use.^{14, 178, 179} The VAS will be used to rate mood, "high" and "liking". The Cannabis Withdrawal Assessment Scale will be utilized at each visit while participants are establishing abstinence from cannabis.

Cannabis craving: The 12-item self-report Marijuana Craving Questionnaire (MCQ-12) will be used to rate craving for cannabis.^{180, 181} We will use the total score for our analyses.

Intellectual Functioning: Study participants will complete the Wide Range Achievement Test – 4 (WRAT-4) reading subtest¹⁸³ at screening as an estimate of premorbid intellectual functioning.

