Common side effects: A "high" feeling (e.g. laughing easily, feeling happy, having a heightened awareness)

Occasional side effects (reported in 3-30% of people): Paranoia, confusion, nervousness, sleepiness, dizziness, stomach pain, nausea with or without vomiting, tachycardia, flushed face

Rare side effects (reported in less than 3% of people): Red eyes, diarrhea and/or incontinence, depression, nightmares, trouble speaking, visual problems, ringing ears, low blood pressure

Seizures have been reported in people taking dronabinol. Patients with a history of a seizure disorder will be excluded from this study.

Recruited patients with dual diagnosis and participants with CUD (without schizophrenia) will all be frequent cannabis users. Thus, we do not expect anything more than minimal effects from the modest dose of THC in the cannabis cigarettes or the two 7.5 mg dronabinol capsules. However, as with the potential of symptom exacerbation in the dual diagnosis patients (above), we will monitor all CUD patients until it is determined by an MD that they can be safely discharged and be prepared to act immediately to provide treatment and to maintain participant safety. Moreover, participants in Groups 1-3 and Groups 5-7 will have a baseline medical history and physical assessment to rule out medical contraindications to administration of dronabinol or cannabis. The assessment will include blood pressure, EKG, complete blood count and blood chemistry screen. All women in the study will have a pregnancy test as described in the section on assessments.

Risk Related to Confidentiality: This research involves monitoring and treatment of patients who use cannabis, an illegal substance. Participants may engage in other illegal activities. Maintaining confidentiality is an area of utmost importance for this population.

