Risks from Cannabis Withdrawal: Heavy cannabis users who discontinue use during the study may experience symptoms of cannabis withdrawal, involving nervousness, sleep disturbance, and appetite changes. Withdrawal from cannabis is not medically dangerous, and does not result in known long-term negative consequences. Since patients with schizophrenia tend to be light users of cannabis, we do not expect substantial cannabis withdrawal symptoms in our dual diagnosis participants. Some CUD (without SCZ) participants, if they are heavier users, may experience some withdrawal symptoms.

Participants will be educated about cannabis withdrawal with a fact sheet that includes a brief list of coping strategies. If participants experience cannabis withdrawal, research staff will cue the participant to use coping strategies and, if needed, will link the patient with clinical support from their treatment team (for patients with SCZ-CUD) or from clinical staff at DHMC (for participants with CUD alone).

Risks to Fetuses and Nursing Infants: Cannabis is known to be harmful to fetuses. Dronabinol is a pregnancy category C medication. The risks of brain fMRI for pregnant or nursing mothers to fetuses and to nursing babies are unknown. Thus, pregnant or nursing mothers will not be included in the study.

A urine pregnancy test, paid for by the study will be given to all women at the initial assessment, and on the morning of each scan day (i.e., thus before administration of cannabis, dronabinol or placebo and before scanning). If a participant is pregnant at baseline or becomes pregnant, she will be informed immediately, referred to her psychiatrist and/or her primary care physician, and discharged from the study. She will not undergo scanning nor be given cannabis or dronabinol.

Risks Related to Genetic Testing: The risks from genetic testing are mostly related to confidentiality and others (e.g. an insurer) learning a participant's results. To protect them from this type of risk, test results will be kept private. Information about participants will be coded with a number, not their name. Only the researchers in this study will be able to know the results of testing. The results of the genetic test will not be told to participants, treatment providers or others outside of the study. The results of the test will not be included in participants' medical records.

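### The exploratory SCZ-CUD versus CUD-only comparisons (Aims 1b and 2c) ignore prior cannabis use, which may differ between these non-randomised groups

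*Combined protocol and SAP*

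**What the plan says.** Section 7b, Aim 1, compares the pooled SCZ-CUD groups (G1-G3) with the single-diagnosis controls at T1. A group ANOVA is to "explore whether they will also differ from control participants with SCZ alone (G4) and control participants with CUD alone (G5, G6 and G7". No covariate is named there. For Aim 2c, Section 7b states: "The two sets of intervention effects (specific to SCZ-CUD and CUD alone) will be compared". Section 3 (Overview) gives the reason for these controls: to begin separating the influence of schizophrenia from that of cannabis use disorder.

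On prior use, Section 5 asks the same of Groups 1-3 and Groups 5-7: a SCID-confirmed cannabis diagnosis and "Use of cannabis within the month prior to screening based on the TLFB". It sets no minimum amount and no matching.

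Section 14 makes two statements about level of use:
- Risks from Cannabis Withdrawal: "Since patients with schizophrenia tend to be light users of cannabis, we do not expect substantial cannabis withdrawal symptoms in our dual diagnosis participants", and "Some CUD (without SCZ) participants, if they are heavier users, may experience some withdrawal symptoms".
- Risks from Cannabis and Dronabinol - Other: "Recruited patients with dual diagnosis and participants with CUD (without schizophrenia) will all be frequent cannabis users".

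Section 10 (Substance Use) names the instrument: "We will use the Timeline Follow-Back (TLFB) calendar to establish use of cannabis or other substances". The plan uses it for eligibility, for confirming abstinence and at the one-week follow-up call. The covariates or controls that the plan does name are smoking (Section 5 note), trauma exposure (Section 10) and cerebral blood flow (Section 7b).

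**The concern.** Participants are randomised to treatment within a diagnosis, but nothing balances cannabis history across diagnoses. The plan's own expectation in the withdrawal text is that history may differ, and the shared entry rule does not prevent this.

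Prior use could act in two places. T1 is measured after about 14 days of required abstinence, which Section 4 allows to be shortened to 7, so use level or residual withdrawal could shift baseline reward measures. At T2, tolerance could change the response to cannabis or dronabinol. The plan reasons this way itself: Section 14 infers from participants' habitual use that the study drugs will have little untoward effect.

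At stake is the interpretation of Aims 1b and 2c. A difference between G1-G3 and G5-G7 may mix diagnosis with cannabis history, and the planned output would not let a reader see how much of each it contains.

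**Working it through.** **1. The plan's own figure.** Section 7c gives at least 80% power at d = 0.7 for Aim 1a, 75 v 25. The significance level is not stated; two-sided 5% is assumed here. SE = sqrt(1/75 + 1/25) = 0.231; 0.7/0.231 = 3.03; power = Phi(3.03 - 1.96) = 86% (noncentral t: 85%). The figure is reproduced and is not in dispute. Section 7c gives no power figure for Aim 1b, and for Aim 2c says only that power is limited.

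**2. Detectable effect for Aim 1b.** With 25 per group (Section 4), the pooled comparison is 75 v 75. Detectable d at 80% power = (1.96 + 0.84) x sqrt(2/75) = 2.80 x 0.163 = 0.46.

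**3. Distortion from use level at T1.** Let g be the difference in mean use between diagnoses, in SD units, and r the within-group correlation of use with the outcome. With no true diagnosis effect, the apparent d is r x g. The documents give neither r nor g, so every row is an assumption.

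| r | g | apparent d | chance of p < 0.05 | detectable d after adjustment |
|---|---|---|---|---|
| 0.2 | 0.5 | 0.10 | 9% | 0.46 |
| 0.3 | 0.5 | 0.15 | 15% | 0.45 |
| 0.2 | 1.0 | 0.20 | 23% | 0.50 |
| 0.3 | 0.8 | 0.24 | 31% | 0.47 |
| 0.3 | 1.0 | 0.30 | 45% | 0.49 |

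For r = 0.2-0.3 and g = 0.5-1.0, d is 0.10-0.30, which is 0.22 to 0.66 of the detectable 0.46. A stronger assumption (r = 0.4, g = 1.0) gives d = 0.40 and 68%.

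**4. Direction.** The sign of r is not known. If heavier use or withdrawal blunts reward response, the CUD-only mean falls and a true SCZ-CUD deficit is masked. If it works the other way, a deficit is exaggerated.

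**5. Cost and benefit of adjustment.** The last column is 2.80 x sqrt((2/75) x (1 - r^2) x V), with V = 1 + g^2 x 37.5/148. For g = 1.0, V = 1.25. Simulated false-positive rates with use as a covariate were about 5% (r = 0.3, g = 0.8 and r = 0.4, g = 1.0), against 30% and 68% without it. This holds for a correctly specified linear model with use measured without error.

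**6. Aim 2c.** The contrast is (G1 - G3) - (G5 - G7) with 25 per arm. In units of the SD of change, SE = sqrt(4/25) = 0.40, so 80% power needs 2.80 x 0.40 = 1.12 SD. An assumed tolerance-driven difference of 0.3-0.5 SD would reach p < 0.05 only 12-24% of the time. The estimate would still be shifted, but a test of use-by-treatment here would be weak.

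**The case against.** The strongest reply is that the documents do not establish a difference in use. Section 14 also calls both populations frequent users, its remark on CUD-only participants is conditional, and both populations must meet a SCID cannabis diagnosis, not be seeking treatment, and achieve the required abstinence. These shared rules narrow the range of use. That stands as a limit on certainty. It does not show that use is equal, and the two Section 14 statements sit uneasily together.

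A second reply is that Aims 1b and 2c are exploratory and Section 7c already concedes limited power for 2c. This stands, and it keeps the point modest. Low power does not remove bias, however, and the T1 comparison pools 75 per side.

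A third is that plasma THC is modelled. It addresses exposure around the session, not tolerance or use history.

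A reader might infer more than the documents support:
- That every participant receives the same T2 exposure, so any difference must be tolerance. G3 and G7 receive placebo only, and cigarette exposure varies with stock strength and stopping point.
- That the plan collects amounts used and ignores them. The TLFB is said to establish use; recording of quantity is not stated.
- That a difference will be reported as specific to schizophrenia. The plan says only that it will explore and compare.

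**Conclusion.** The point holds in a limited form. The comparisons of G1-G3 with G5-G7 at T1, and of their drug effects, are between non-randomised groups whose prior use may differ, and no planned group analysis takes prior use into account. The bias could create or hide a difference. Its size is unknown: d = 0.10-0.30 at T1 rests entirely on the assumed r and g.

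It would be wrong to read this as undermining the main results. Aim 1a does not involve the CUD-only groups, and the randomised contrasts within a diagnosis (G1 or G2 v G3; G5 or G6 v G7) are not confounded by use level. This is an inexpensive improvement to exploratory analyses, not a flaw in the trial's central tests.

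**What to change.** - Report TLFB days of cannabis use in the month before screening, by group.
- Pre-specify that variable as a covariate in a sensitivity analysis of G1-G3 v G5-G7 at T1, shown beside the unadjusted result.
- For Aim 2c, label any use-by-treatment term as exploratory only.
- State that where the adjusted and unadjusted estimates disagree, or use overlaps little between diagnoses, the difference will not be attributed to schizophrenia alone.
- Reconcile the two Section 14 statements on level of use.

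The cost is SAP wording and one extra model on data needed for eligibility. Intervals widen slightly if use differs strongly by diagnosis: detectable d moves from 0.46 to at most about 0.50 in the cases above. Adjustment may be incomplete, because days used omits quantity and duration and Section 4 allows up to 10 weeks between screening and T1. It may also over-adjust if lighter use is part of the illness. Showing both estimates makes these limits visible.
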